# **8 TREATMENT OF PATIENTS**

## **8.1 Study Drug Administration**

For each individual patient, in the 50 mg cohort (Cohort A), Study Drug will be administered SC as a single 0.5 mL injection once every 4 weeks during Weeks 1-49 for a total of 13 doses. For each individual patient in the 80 mg cohort (Cohort B), Study Drug will be administered SC as a single 0.8 mL injection once every 4 weeks during Weeks 1-49 for a total of 13 doses. Self-administration will be allowed after appropriate training of patient and/or caregiver.

Please refer to the Study Drug Manual provided by the Sponsor for more detailed instructions for Study Drug (ISIS 678354 or placebo) preparation, administration, and patient observation post-Study Drug administration.

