## **8.7 Discontinuation of Study Drug Administration**

Reasons for permanent discontinuation of Study Drug administration are:

- The patient experiences an AE that necessitates permanent discontinuation of Study Drug

- At the discretion of the Investigator due to a safety concern
- At the patient's request due to an adverse event
- The patient develops laboratory test abnormalities that meet any of the stopping rules listed in Section 8.5
- The patient becomes pregnant. Report the pregnancy according to instructions in Section 9.5.4
- Reasons not related to an AE
  - Patient request to stop Study Drug but continue study participation
  - The patient withdraws consent for study participation
  - Investigator decision (e.g., non-compliant patient)
  - Sponsor decision

The reason for discontinuation of Study Drug must be recorded in the eCRF and source documentation. If the Investigator decides that discontinuation of Study Drug is warranted, the Investigator should make every effort to contact the Sponsor or TIMI Hotline prior to discontinuation of Study Drug.

Patients who had Study Drug administration discontinued for any reason other than full withdrawal of consent for study participation should continue their participation in the study, attending visits and procedures as per Section 8.7.1, if possible, and providing survival status by the end of the trial. If the patient declines or is unable to attend study visits, the Investigator should clarify what type of follow-up the patient is agreeable to: in person, by phone/mail, through family/friends, via correspondence/communication with other physicians, and/or from review of the medical records, and as allowed per local regulations. Wherever possible these patients should continue to be followed up via the agreed means to collect information on AE, concomitant medications and survival status. At the very least, the patient's status at the end of the Treatment Period should be ascertained and documented wherever possible. The agreed means of follow-up will be documented in the patient records and notified to the Sponsor.

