The efficacy summaries will be presented by the treatment group (placebo, olezarsen 50 mg, olezarsen 80 mg). The disposition, demographics, baseline characteristics, medical history, prior and concomitant medications, and protocol deviations will be presented by treatment group, total olezarsen treated (50 mg + 80 mg) and overall. The safety data will be presented by the treatment group and total olezarsen treated.

All tables and figures containing efficacy endpoints will indicate whether they present raw data or adjusted results from the statistical model, with footnotes indicating the model used and covariates included in the model.

Selected safety endpoints will be analyzed using below analysis method:

- The crude incidence rates, risk difference with 95% CI between each active treatment group (or total olezarsen treated) and pooled placebo group. The crude incidence rate (in percentage) is defined as the number of patients who experienced at least one event times 100 divided by the total number of patients. The 95% CI of risk difference in crude incidence rate will be estimated using the unstratified Miettinen-Nurminen (MN) method.
- Exposure-adjusted incidence rate (EAIR) rates, EAIR difference with 95% CI between each active treatment group (or total olezarsen treated) and pooled placebo group. EAIR is defined as the number of patients who experienced at least one event times 100 divided by total person-years at risk for the event. For patients with events, the time at risk is the time from the first dose date to the first onset of an event (i.e., first event date minus first dose date plus one day divided by 365.25); for patients with no event, the time at risk is the total duration in the on-study period in year (i.e., last participation date or data cutoff date minus first dose date plus one day divided by 365.25). The difference of EAIR and 95% CI will be estimated using Wald's method.
- Exposure-adjusted event rate (EAER), defined as the number of events times 100 divided by the total duration in the on-study period in year.

All tables, figures and data listings to be included in the report will be independently checked for consistency, integrity and in accordance with standard Medpace (a CRO that is responsible for pre-programming datasets and TLFs for the Study) procedures.

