**For end dates:**

Imputation will be performed for the end date only if the day or month is missing (i.e., year is present) for a resolved AE as follows:

- If month and day are missing and year is:
  - the same as the year of the last dose of Study Drug, then assign the month-day of the last dose of Study Drug
  - otherwise, assign December 31
- If only day is missing, then assign the last day of the month.

If the imputed start date is later than the imputed end date, then set the imputed start date to the imputed end date.

*4.10.2.4 Adverse Events of Special Interest*

The following AEs are considered AE of special interest for the study. These events will be reviewed and evaluated to determine if they meet the criteria.

- Platelet count < 50,000/mm^3 accompanied by a major bleeding (MB) event or clinically relevant non-major bleeding (CRNMB) event, or platelet count of < 25,000/mm^3 irrespective of a MB or CRNMB event.
- Use of medications (prophylactic treatment such as antihistamines, acetaminophen, non-steroidal anti-inflammatory drugs [NSAIDs], corticosteroids, etc.) as pre-treatment to avoid a hypersensitivity reaction or recurrence of a previous hypersensitivity reaction.

Those events will be individually reviewed and evaluated to determine if they meet the criteria.

The following analyses will be provided.

- The number and percentage of patients experiencing events as well as the total number of reported events, risk difference and its 95% CI in the crude incidence rates between each active treatment group (or total olezarsen treated) and pooled placebo group, classified by PT, will be tabulated by treatment group and total olezarsen treated.
- A cumulative incidence plot if data supported.
- EAIR, risk difference and its 95% CI in EAIRs between each active treatment group (or total olezarsen treated) and pooled placebo group, and EAER. classified by PT, will be tabulated by treatment group and total olezarsen treated.

*4.10.2.5 Other Adverse Events of Interest*

The number and percentage of patients experiencing events as well as the number of reported events, risk difference and its 95% CI in the crude incidence rates between each active treatment group (or total olezarsen treated) and pooled placebo group, classified by PT (unless otherwise specified), will be tabulated by treatment group for the following AEs of Interest.

*4.10.2.5.1 Bleeding TEAEs*

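### The exposure-adjusted rates for the hypersensitivity pre-treatment AESI count time after the last injection, when the event can no longer occur, so the rate per year comes out too low

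*Combined protocol and SAP*

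**What the plan says.** SAP 4.2.1 (Data Presentation) defines EAIR as patients with at least one event, times 100, "divided by total person-years at risk for the event". It then makes that denominator operational in two parts:

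- "For patients with events, the time at risk is the time from the first dose date to the first onset of an event".
- "for patients with no event, the time at risk is the total duration in the on-study period in year", which it spells out as "last participation date or data cutoff date minus first dose date plus one day divided by 365.25".

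EAER is the number of events times 100 over total on-study time, for all patients. The SAP neither defines the on-study period nor states a cutoff date. The protocol's Study Glossary has a patient on study until the last study visit, which includes follow-up.

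SAP 4.10.2.4 lists two AESIs. The second is use of medication "as pre-treatment to avoid a hypersensitivity reaction or recurrence of a previous hypersensitivity reaction". For the AESIs the SAP plans crude incidence with a risk difference, a cumulative incidence plot if the data support one, and "EAIR, risk difference and its 95% CI in EAIRs between each active treatment group (or total olezarsen treated) and pooled placebo group, and EAER".

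Protocol 8.1 gives Study Drug "once every 4 weeks during Weeks 1-49 for a total of 13 doses". Appendix A puts Week 49 at Day 337, Week 53 at Day 365, and the last follow-up visit 91 days after the end of treatment. Under Protocol 8.7, patients who stop drug without fully withdrawing consent "should continue their participation in the study", and Protocol 8.7.1 encourages them to attend the landmark visits up to Week 53.

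**The concern.** Pre-treatment presupposes an injection still to come. After a patient's last dose this AESI cannot occur, yet the SAP keeps counting that patient's time: the four weeks to the end of treatment, the 13-week follow-up and, for a patient who stops drug but stays in the study, the remaining time to Week 53. The calculation therefore departs from the SAP's own statement that EAIR is per person-time at risk for the event.

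At stake are the level of a reported safety rate and the EAIR differences built on it. Both are pulled towards zero. The pull is stronger in an arm where more patients stop drug and remain on study. Protocol 8.5.6 says discontinuation should be recommended once a hypersensitivity reaction is established, so some of the added time may come from the patients most relevant to this signal.

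The other events to which the SAP applies these rates, the platelet AESI and MACE, can occur after dosing ends. A common on-study denominator suits them.

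**Working it through.** The documents state no expected rate or person-time total for this AESI, so there is no planned figure to reproduce. The check rebuilds the schedule and compares time at risk with the time the SAP counts.

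**Schedule**

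- Dose k falls on Day 1 + 28(k − 1), so dose 13 is on Day 1 + 28 × 12 = 337.
- End of treatment: 337 + 28 = Day 365.
- End of follow-up: 365 + 91 = Day 456.
- On-study time by the SAP formula: 456 − 1 + 1 = 456 days.

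**Formula.** Understatement = 1 − (days from first to last dose) / (on-study days counted).

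**Completer.** 1 − 337/456 = 1 − 0.739 = 26.1%.

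**With 20% stopping early.** The 20% is the dropout figure in Protocol 10.2. That the last dose is spread evenly over doses 1 to 12 (Days 1, 29, …, 309) is an assumption; it gives a mean last-dose day of (1 + 309)/2 = 155. Mean time at risk is 0.8 × 337 + 0.2 × 155 = 300.6 days. The denominator depends on how long these patients stay:

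| Early stoppers | Their mean on-study days | Overall mean on-study days | Ratio | Understated by |
|---|---|---|---|---|
| Stay to Week 53, or to the end of their 13-week follow-up if later | 373.75 | 0.8 × 456 + 0.2 × 373.75 = 439.55 | 0.684 | 31.6% |
| Do only the 13-week follow-up (last dose + 119 days) | 274 | 0.8 × 456 + 0.2 × 274 = 419.6 | 0.716 | 28.4% |
| Leave at the last dose | 155 | 0.8 × 456 + 0.2 × 155 = 395.8 | 0.759 | 24.1% |

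**If all data were cut at Week 53 (Day 365).** Completers: 1 − 337/365 = 7.7%. With 20% stopping drug but staying to Day 365: 1 − 300.6/365 = 17.6%.

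**Other risk windows, completers**

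- Risk runs to the end of the Treatment Period: 1 − 365/456 = 20.0%.
- Risk starts only at the second dose (Days 29 to 337, 309 days): 1 − 309/456 = 32.2%.

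**Effect of stopping the EAIR clock at the first event.** Assume events spread evenly over doses 2 to 13 (mean Day 183).

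- 5% of patients with the event: 1 − (0.95 × 337 + 0.05 × 183)/(0.95 × 456 + 0.05 × 183) = 1 − 329.3/442.35 = 25.6%.
- 20% with the event: 1 − 306.2/401.4 = 23.7%.

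EAIR and EAER are therefore affected almost equally while events are rare.

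**Illustration.** One olezarsen arm has 152 × 1/2 × 3/4 = 57 patients. Assume all complete and there are 3 events.

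- As planned: 100 × 3/(57 × 456/365.25) = 4.2 per 100 patient-years.
- On Days 1 to 337: 100 × 3/(57 × 337/365.25) = 5.7 per 100 patient-years.

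**The case against.** The strongest reply is that little depends on these rates. SAP 4.10.2.4 also gives patient counts, event counts, crude incidence and its risk difference for the same AESI, and none of these uses person-time. SAP 4.10.2.5.3 analyses hypersensitivity events separately, and SAP 4.10.1 reports the number of doses by arm. The AESI rates are outside the testing hierarchy. In the illustration, a Wald interval around 4.2 runs from about −0.6 to 9.0 (4.2 ± 1.96 × 4.2/√3), far wider than the move to 5.7. If the dilution is equal across arms, an EAIR difference and its standard error shrink by about the same factor, so whether the interval excludes zero hardly changes. All of this stands, and it is why the point is minor.

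A second reply is that the size depends on choices. With no cutoff date, the dilution could be as low as about 8% for completers. The 20% in the protocol is a dropout allowance for sample size, and those patients may leave rather than stay to Week 53. That the event needs a coming injection is inferred from the word pre-treatment; neither document says so outright. These limits also stand, and the range above reflects them. The inference remains the natural reading.

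Third, the days from first to last dose are not a perfect denominator either: a patient with a single dose would contribute one day. That favours a per-injection rate. It does not defend on-study time.

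A reader might go further and infer a bias in olezarsen's favour. The documents do not support that as a finding. They plan EAIR differences and no rate ratio, and they give one overall dropout figure with no split by arm. Under an invented 30% versus 10% stopping drug but staying on study, the ratios would be 0.655 and 0.712, and a rate ratio would move by 1 − 0.655/0.712 = 8%. That depends wholly on the invented split.

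**Conclusion.** The point holds as a minor one. For the pre-treatment AESI, the planned EAER for all patients, and the planned EAIR through patients without the event, include time in which the event cannot happen. This conflicts with the SAP's own definition of EAIR.

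The yearly rate is understated by about 26% for completers with full follow-up. It is about 24% to 32% with 20% stopping drug early, under the uniform last-dose assumption and depending on how long those patients stay. A Week 53 cutoff would bring it to about 8% for completers and up to 18% with 20% stopping.

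Absolute rates and EAIR differences shrink by about the same factor in every arm, and more in an arm where more patients stop drug but remain on study. It would be wrong to read this as the AESI being hidden or as a demonstrated advantage to either arm: the crude analyses are intact, no rate ratio is planned, and the rates are descriptive.

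**What to change.** Add one sentence to SAP 4.10.2.4, for this AESI only, choosing one of two options:

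- Report it per injection, as SAP 4.10.2.5.6 to 4.10.2.5.8 already do for local cutaneous, injection-site and flu-like reactions. This is the cleaner choice, because it matches how the event arises and avoids the one-day denominator for single-dose patients.
- Keep a rate per year, but end time at risk at the last Study Drug injection (or at the first event, if earlier, for EAIR). For EAER use first dose to last injection.

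Keep on-study time for the platelet AESI, which can occur during follow-up.

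The cost is that sentence and one derived date, or the injection counts that SAP 4.10.1 already summarises. No efficacy test, alpha allocation, data collection or patient management changes. The downside is that the two AESIs will have different denominators, which needs a table footnote, and that this rate will be reported as higher.

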ISIS 678354 was well-tolerated, there was low incidence of predominantly mild injection site reactions (12.2% vs. 4.2%), and flu-like reactions (8.9% vs. 8.3%) in patients treated with ISIS 678354 compared to placebo, respectively. No dose- or time-dependent changes in platelet (PLT) count were observed, and no patient had a confirmed PLT count  $< 100,000/\text{mm}^3$ . No patient met any liver monitoring rules including increase in ALT or AST  $> 3 \times \text{ULN}$ , or  $> 2 \times \text{baseline}$  (if baseline  $> \times \text{ULN}$ ). The incidence of patients meeting any renal monitoring rules (decrease from Baseline in Estimated GFR [eGFR]  $> 25\%$ , increase in serum creatinine  $> 0.3$  mg/dL, urine albumin/creatinine ratio (UACR)  $> 250$  mg/g, urine protein/creatinine ratio (UPCR)  $> 500$  mg/g) was comparable between the pooled placebo group (20.8%) and the pooled ISIS 678354 group (17.8%).

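### The Wald interval planned for differences in exposure-adjusted incidence of the AESIs takes no account of an arm with zero events

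*Combined protocol and SAP*

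**What the plan says.** SAP 4.2.1 sets two interval methods for selected safety endpoints.

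- For the crude risk difference, the 95% CI "will be estimated using the unstratified Miettinen-Nurminen (MN) method".
- For the rate scale, "EAIR is defined as the number of patients who experienced at least one event times 100 divided by total person-years at risk for the event". On the denominator, "for patients with no event, the time at risk is the total duration in the on-study period in year". The interval for the difference is then fixed in one sentence: "The difference of EAIR and 95% CI will be estimated using Wald's method". No variance formula, continuity correction or zero-event rule follows.

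SAP 4.10.2.4 asks for both scales for the AESIs, by preferred term. The rate-scale item reads "EAIR, risk difference and its 95% CI in EAIRs between each active treatment group (or total olezarsen treated) and pooled placebo group". It is the only section that names an interval for an EAIR difference; for MACE, SAP 4.11.3.1 only summarises the rates.

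There are two AESIs. The first is a platelet count below 50,000/mm³ "accompanied by a major bleeding (MB) event or clinically relevant non-major bleeding (CRNMB) event, or platelet count of" below 25,000/mm³ whether or not there is bleeding. The second is medication given "as pre-treatment to avoid a hypersensitivity reaction or recurrence of a previous hypersensitivity reaction". On the first, Protocol 2.3.4 reports from Phase 2: "No dose- or time-dependent changes in platelet (PLT) count were observed, and no patient had a confirmed PLT count" below 100,000/mm³.

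**The concern.** A Wald interval for a rate difference estimates each arm's variance from that arm's own event count. When the count is zero, the estimated variance is zero, and the interval treats that arm's rate as known exactly. For rare events in arms of 57, 57 and 38 patients, zero counts are the ordinary case.

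The error can go either way. With no events on either side the interval collapses to a point, which looks like precise evidence of no difference. With a few events on olezarsen and none on placebo, all the placebo uncertainty is lost and the interval can exclude zero on very little evidence. At stake is the accuracy of the interval printed for the two events that the protocol singles out for special attention.

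**Working it through.** The plan states no figure for this interval, so there is none to reproduce. The check compares the Wald interval with a score interval at plausible counts.

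**Inputs**
- 152 patients, randomised 1:1 to cohorts and then 3:1 within cohort (SAP 3.1): 57 on 50 mg, 57 on 80 mg, 38 on pooled placebo.
- On-study time for a completer: Day 365 plus 91 days of follow-up (Protocol Appendix A) = 456 days.
- Person-years (PY) without dropout: 57 × 456/365.25 = 71.2 per active arm, 142.3 for total olezarsen, 38 × 456/365.25 = 47.4 for placebo.
- Lower end of the range: about 57 and 38 PY. This is reached either with 20% less exposure (0.8 × 71.2 = 57.0; 0.8 × 47.4 = 37.9; Protocol 10.2 gives about 20% dropout) or by counting only the treatment period (57 × 365/365.25 = 57.0).

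**Formulas**, with x events in T person-years, subscript 1 for olezarsen and 0 for placebo, and d = x1/T1 - x0/T0
- Wald (standard unadjusted Poisson form, assumed): d ± 1.96 × √(x1/T1² + x0/T0²).
- Score: all values δ for which |d - δ| ≤ 1.96 × √(λ1/T1 + λ0/T0), where λ1 and λ0 are the rates fitted under λ1 - λ0 = δ.

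**No events in either arm.** The Wald standard error is √0 = 0, so the interval is 0.0 to 0.0 at any exposure. The score limits reduce to -1.96²/T0 and +1.96²/T1. For one active arm these are -3.84/47.4 = -8.1 and 3.84/71.2 = 5.4 per 100 PY.

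**Events on olezarsen only.** The Wald interval is (x1 ± 1.96√x1)/T1, and T0 does not appear. It excludes zero once x1 > 1.96² = 3.84, that is from four events, whatever the placebo exposure. The lower score limit is x1/T1 - 1.96²/T0, so placebo exposure does count. It excludes zero only when x1 > 3.84 × T1/T0. That takes 6 events against none for one active arm (T1/T0 = 1.5) and 12 against none for total olezarsen (T1/T0 = 3).

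Results per 100 PY:

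| Comparison | PY | Events | Wald 95% CI | Score 95% CI |
|---|---|---|---|---|
| One active arm vs placebo | 71.2 vs 47.4 | 0 vs 0 | 0.0 to 0.0 | -8.1 to 5.4 |
| | | 1 vs 0 | -1.4 to 4.2 | -6.7 to 8.0 |
| | | 2 vs 0 | -1.1 to 6.7 | -5.3 to 10.3 |
| | about 57 vs 38 | 0 vs 0 | 0.0 to 0.0 | -10.1 to 6.7 |
| Total olezarsen vs placebo | 142.3 vs 47.4 | 0 vs 0 | 0.0 to 0.0 | -8.1 to 2.7 |
| | | 4 vs 0 | 0.06 to 5.6 | -5.3 to 7.2 |

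In the last row, if the true rates were equal, all four events would fall on olezarsen with probability 0.75⁴ = 32%. The score statistic for no difference is √(4 × 47.4/142.3) = 1.15.

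**How often this arises.** For one active arm and placebo with the same true rate r, the chance that both have no events is exp(-r × 118.6). The chance that at least one has none is 1 - (1 - exp(-71.2r))(1 - exp(-47.4r)).

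| True rate per 100 PY | Both arms zero | At least one arm zero |
|---|---|---|
| 0.1 | 89% | 99.7% |
| 0.5 | 55% | 94% |
| 1 | 31% | 81% |
| 2 | 9% | 53% |

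If the olezarsen rate is three times placebo, Wald coverage of the true difference, enumerated from the Poisson distributions, is 23%, 73% and 91% at placebo rates of 0.1, 0.5 and 1 per 100 PY. Score coverage there is 99 to 100%. From 2 per 100 PY upwards, Wald coverage is about 94 to 97%, under equal or threefold rates.

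**The case against.** The strongest reply is that little hangs on this interval. SAP 4.10.2.4 already asks for the crude risk difference of the same AESIs in the same comparisons, with the Miettinen-Nurminen interval. At 0/57 against 0/38 that gives -9.3% to 6.4%, and at 4/114 against 0/38 it gives -5.8% to 8.7%. The AESIs are also reviewed individually. No test, threshold or multiplicity step uses the EAIR difference. All of this stands and limits the consequence, but it does not make the EAIR interval right.

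A second reply is that the defect is conditional. It needs an arm with no events, and a preferred term with no events in any group may never get a table row. This also stands in part. A 0 vs 0 comparison can still be displayed, because an event seen only on 80 mg leaves the 50 mg against placebo row at 0 vs 0. The evidence that events will be rare is limited: the Phase 2 platelet finding comes from 114 patients at doses up to 50 mg, and nothing is said about how often pre-treatment against hypersensitivity will be needed.

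A reader might infer more than the documents support:

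- That the report would show certainty of no excess risk. It would not, because the crude interval for the same events stays wide.
- That the two intervals would contradict each other in one table. The SAP lists them as separate items and does not say that they share a table. They also estimate different quantities, a proportion and a rate. At 4 vs 0 one would exclude zero and the other would not, which is awkward to explain but comes from the method.
- That the exact upper limit for zero placebo events, about 7.8 per 100 PY at 47.4 PY, measures the excess risk that the trial cannot rule out. It bounds the placebo rate. At 0 vs 0 the upper score limit for excess risk is 5.4 for one arm and 2.7 for total olezarsen.

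**Conclusion.** The point holds, with a modest consequence. Followed as written, SAP 4.2.1 gives a wrong interval for the EAIR difference whenever a compared arm has no events: zero width at 0 vs 0, and an interval blind to placebo exposure when only olezarsen has events. In the second case four events are enough to exclude zero, where a score interval would need six for one active arm or twelve for total olezarsen.

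This rests on the standard unadjusted Poisson variance, because the SAP does not write its formula, and on the assumed person-years for the sizes shown. Neither the zero-width result nor the four-event threshold depends on exposure, and the lower end of the range makes the score intervals wider. Zero-event arms are likely for the platelet AESI; for the pre-treatment AESI the documents do not allow a statement. Since the summary is descriptive and a valid crude-scale interval is planned beside it, this should be corrected, but it does not threaten any conclusion of the trial.

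**What to change.** In SAP 4.2.1, replace Wald's method by a Miettinen-Nurminen type score interval for a difference of Poisson rates, to be used for the AESI EAIR differences in SAP 4.10.2.4. This matches the method already chosen for crude risk differences. An exact interval would also do; at the least, the SAP should say what is reported when an arm has no events.

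The cost is one SAP sentence and a short validated macro. Intervals become wider and, when events are sparse, somewhat conservative: score coverage was 99 to 100% in the sparse scenarios above. Data collection, sample size and the efficacy analyses are unaffected.
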